3 rd Simulation 13.30-14.00	1 x Doctor 1 x Therapist 2 x Nursing Team	1 x Doctor 1 x Therapist 2 x Nursing Team	1 x Doctor 1 x Therapist 2 x Nursing Team	1 x Doctor 1 x Therapist 2 x Nursing Team	1 x Doctor 1 x Therapist 2 x Nursing Team	1 x Doctor 1 x Therapist 2 x Nursing Team	1 x Doctor 1 x Therapist 2 x Nursing Team	1 x Doctor 1 x Therapist 2 x Nursing Team	Up to 32 participants
4 th Simulation 14.30-15.00	1 x Doctor 1 x Therapist 2 x Nursing Team	1 x Doctor 1 x Therapist 2 x Nursing Team	1 x Doctor 1 x Therapist 2 x Nursing Team	1 x Doctor 1 x Therapist 2 x Nursing Team	1 x Doctor 1 x Therapist 2 x Nursing Team	1 x Doctor 1 x Therapist 2 x Nursing Team	1 x Doctor 1 x Therapist 2 x Nursing Team	1 x Doctor 1 x Therapist 2 x Nursing Team	Up to 32 participants
Focus Group 15.00-17.00	8 Participants from the 2 afternoon Simulations discuss the simulation together								Up to 8 datasets
									Up to 128 Participants in Total
									Up to 16 datasets

Figure 2

STUDY MANAGEMENT

The investigator will lead a study management group consisting of the Chief investigator and 2 coinvestigators. The Principle investigator or delegated local collaborator from each Trust involved will be invited to join the group for updates and any concerns. The group will meet monthly to discuss progress and amendments as required.

The Chief Investigator has overall responsibility for the study and shall oversee all study management.

The data custodian will be the Chief Investigator.

DURATION OF THE STUDY AND PARTICIPANT INVOLVEMENT

Study Duration:

Enrolment to the study will begin as soon as enquiries are received from the invitations and will be completed within 6 months when up to 32 simulations and up to 16 focus groups have been analysed and collectively themed. Analysis of data will be presented back to participants to verify interpretation. The extended timeline is to account for the winter period where operational pressures in hospital may cause delays to rostering participants.

Participant Duration:

Active Involvement: Each participant will be required for a Maximum of 4 hours.

Consent:	20 mins	}	All on same day on an agreed date at time of consent
Simulation:	30 mins		
Reconsent:	5 min		
Focus Group:	60-90 mins		
Follow up:	30 minutes		Separate day within 2 months of Sim and focus group

End of the Study

The end of the study will be the last feedback session of the last participant.

SELECTION AND WITHDRAWAL OF PARTICIPANTS

Recruitment

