Participants will be recruited from medical and surgical wards at up to 4 acute Trusts (*Figure 2*). Medical and surgical wards will be selected as they have regular exposure to patients who are 65 and over and patients with specific underlying conditions between the age of 50 and 65 who are considered at high risk of falls (National Institute for Health and Care Excellence, 2019). The initial approach will be from a member of the staff's management team who will include the participant information sheet. Information will also be on display in the relevant staff only clinical areas (ie staff rest and study areas). The participants will self-select by contacting the investigator via email, whats app, QR code or phone. The QR code leads to a quick microsoft form which gives the potential participant chance to check they meet the inclusion criteria and give the Investigator their contact email address or phone number. This form is sent to the Investigator's Microsoft forms 365 account and it automatically emails me to let me know there is a response waiting for me.

The investigator will inform the participant of all aspects pertaining to participation in the study.

As the participants are all healthcare professionals or associated roles, working in the NHS there is, a requirement for them to be fluent in English both written and oral. It is reasonable, therefore, to assume they can communicate in English and therefore interpreters will not be required.

It will be explained to the potential participant that entry into the study is entirely voluntary and that their employment rights will not be affected by their decision. It will also be explained that they can withdraw at any time but attempts will be made to avoid this occurrence. In the event of their withdrawal it will be explained that their data collected so far cannot be erased and we will seek consent to use the data in the final analyses where appropriate.

Eligibility criteria

Inclusion criteria

Potential participants need to meet at least one of the inclusion criteria below:

- Any healthcare professional or associated support staff involved in the fall risk assessment of patients on admission to a standard care ward environment in hospital
- Any healthcare professional or associated support staff involved in the multifactorial assessment of patients in an acute ward environment

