Following the simulation the participants will be informed that the exact nature of the research enquiry is fall prevention in hospitals. The researcher is deliberately using the term 'patient safety' rather than falls prevention prior to the simulation as it is preferred that the staff are not aware of the research detail until after they participate in the simulation. Whilst it is recognised by cognitive load theory that individuals will be able to perform better with forewarning of scenarios (Cox et al., 2017) and therefore learn more easily, the intention of this simulated

scenario is to understand behaviour in the workplace. In the workplace the nurse will not always know what is going to happen next so withholding this information is a closer replication of the workplace environment and may offer a better opportunity to experience workarounds and habits as the nurse reverts to 'work as done' rather than work as 'imagined' (Hollnagel Erik, 2012). This is not totally misleading the participants as fall prevention is part of patient safety which is used as an umbrella term and is a common situation they find themselves in at work.

The investigator considered other research methods such as observational studies but a patient fall is an infrequent occurrence so having an opportunity to observe one in practice would be difficult. As the investigator is also a registered nurse they would be obliged to prevent a patient falling rather than observe it. It would also not offer a shared experience where critical decision method can be used to extract key decision points. Simulation offers a safe and comfortable alternative where staff can reflect on their actions and discuss with peers, drawing from and sharing their real life experiences keeping them safe from judgement, emotional distress, personal responsibility and blame.

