- contact details. The TRL will be kept securely in a password protected file on UoN one drive.
6. Potential participants who choose not to go into the study will only be on the TRL as their unique identifier and their reason for not participating if they give one but they will not be asked. All personal identifying details will be deleted immediately. The investigator will not attempt to contact them again.
 7. Participants who are happy to continue into the study will choose 1 of 2 dates possible for the simulation and focus group.
 8. Details of location and agenda for the simulation and focus group will be sent to the participant.
 9. All participants will be contacted by phone or email via their preferred form of communication identified when recruited at step 5 to remind them the day before the simulation and focus group.
 10. Participants will arrive at the simulation lab and will be given a pseudonym, name badge and role card (the pseudonym is to use during the simulation and recording to protect their identity to other participants and on the recording). The pseudonym will also be recorded alongside their unique identifying number and demographics on the TRL. The TRL will be kept securely in a password protected file on UoN one drive in accordance with the data management plan (DMP).
 11. The investigator will observe with notes during the simulation (30 mins). This will be recorded.
 12. On completion of the simulation the investigator will re-consent the participant as they will now realise that the patient safety theme was fall prevention. (5 mins)
 13. On completion of the **re-consent process** a guided critical decision method session will detail the timeline of events and key decisions (30 mins). This will be recorded on University of Nottingham property Dictaphones and the data securely saved as per the DMP.
 14. On completion of the timeline, the semi structured focus group will begin, facilitated by the investigator. This will be recorded on University of Nottingham property Dictaphones and the data securely saved as per the DMP.
 15. The investigator will close the discussion group and explain that the participant will be contacted again in order to share the analysis and themes to verify an accurate understanding of discussion. Participant will be given the option to opt out of this stage.
 16. Investigator will transcribe and analyse themes evolving from the session using Nvivo14.

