The participant will be invited to play their usual professional role in a 30 minute scenario depicted by simulation and will be run 8 times over 2 separate days in each Trust using an actor. Using the safety of 'a simulation of a fall in an acute setting' rather than observations in practice the investigator will observe the participants behaviour and actions during the simulation of a patient having an accidental fall. Abdulmohdi and McVicar (2023) found there was a significant increase in deduction and analysis when using simulation compared to observations in practice. An additional advantage of a simulation is that the participants can be more confident in their discussion without the need to defend team culture compared to being observed in clinical practice. It is also easier to create the patient fall safely thereby maintaining the least powerful position for the investigator, as feedback in a hypothetical situation has not resulted in patient harm or reflected on their practice so the feeling of being judged is avoided (Humphries, 2003). There is also no compelling professionalism to require the investigator to prevent a participant causing harm to a patient or to draw attention to an omission heightening the potential power dynamic between researcher and participants (Humphries, 2003). The simulation will be held on the Trust premises to ensure ease of access for participants and minimise time away from clinical practice.

Following completion of the simulated scenario a 90 minute debrief focus group will reflect on the impact of the simulation and hear from the participants how this relates to their experience in practice. Michie et al. (2011) recommends a three-step process to investigate behaviour and this will be used as a framework for the focus group discussion alongside Critical Decision Making (CDM) (Weitzenfeld J.S, 1990). The investigator will use a semi structured design.

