The incident portrayed in the simulation can evoke strong emotions either from previous professional or personal experience. Should a participant become distressed the investigator will initiate the distress protocol.

It is not anticipated that the confidentiality of participants will be breached however it is likely that participants may know each other and/or are working with or have worked with each other previously. Whilst a confidentiality agreement will be discussed with each participant and a request not to share any information outside the simulation lab and focus group room there is a chance that this will happen. In this instance the participants will be asked to report this to the investigator who will approach the relevant senior team in the hospital. Depending on the nature of the issue and the available evidence the senior management team will take appropriate action. An apology will be offered where appropriate to the affected participant.

ETHICS COMMITTEE AND REGULATORY APPROVALS

The study will not be initiated before the protocol, consent forms and participant information sheets have received approval / favourable opinion from the Research Ethics Committee (REC), the respective National Health Service (NHS) or other healthcare provider's Research & Development (R&D) department, and the Health Research Authority (HRA) if required. Should a protocol amendment be made that requires REC approval, the changes in the protocol will not be instituted until the amendment and revised informed consent forms and participant information sheets have been reviewed and received approval / favourable opinion from the REC and R&D departments. A protocol amendment intended to eliminate an apparent immediate hazard to participants may be implemented immediately providing that the REC are notified as soon as possible and an approval is requested. Minor protocol amendments only for logistical or administrative changes may be implemented immediately; and the REC will be informed.

The study will be conducted in accordance with the ethical principles that have their origin in the Declaration of Helsinki, 1996; the principles of Good Clinical Practice and the UK Department of Health Policy Framework for Health and Social Care, 2017.

INFORMED CONSENT AND PARTICIPANT INFORMATION

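### The QR screening form and the repeat-run timetable may let staff learn the falls topic before their simulation, and nothing records who knew

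*Combined protocol and SAP*

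**What the plan says.** **Concealment.** The Informed consent section, under Selection and Withdrawal of Participants, explains that patient safety is used as an umbrella term on purpose, because "it is preferred that the staff are not aware of the research detail until after they participate in the simulation". The stated reason is that unwarned staff may show their habitual practice and workarounds.

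**Screening.** Under Recruitment, and again at step 2 of Study Regimen: "The QR code leads to a quick microsoft form which gives the potential participant chance to check they meet the inclusion criteria". The Inclusion criteria list four role criteria plus ability to consent. The first role criterion begins "Any healthcare professional or associated support staff involved in the fall risk assessment of patients on admission". Two others name fall prevention measures and care after an accidental fall. The fourth names only multifactorial assessment.

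**Disclosure.** Step 12 of Study Regimen: "On completion of the simulation the investigator will re-consent the participant as they will now realise that the patient safety theme was fall prevention". The Informed consent section places this private re-consent anywhere between the simulation and the focus group.

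**Repetition.** The Methods section says the scenario "will be run 8 times over 2 separate days in each Trust using an actor". Figure 2, under Study Configuration, gives the times.

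**Safeguard.** Ethical and Regulatory Aspects provides for a confidentiality agreement discussed with each participant and adds "a request not to share any information outside the simulation lab and focus group room there is a chance that this will happen". Breaches are to be reported to the investigator and taken to senior hospital staff.

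**The concern.** The plan withholds the topic at first consent and gives one main reason: to see practice without forewarning. If staff can learn the topic beforehand, from the form or from colleagues, that benefit is reduced while the withholding remains.

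The notes and decision timeline from a forewarned group would look the same on paper as those from an unwarned one. No step asks who already knew, and no step carries run order into the analysis. The primary objective asks whether experience is universal, and sampling continues until themes repeat or do not. If a later group acts on what an earlier group told it, similar behaviour within a Trust could be read as shared experience.

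**Working it through.** **Step 1: reproduce the plan's totals.** Inputs: up to 4 Trusts (Recruitment: "Participants will be recruited from medical and surgical wards at up to 4 acute Trusts"), 2 days per Trust, 4 simulations per day, and 4 participants per simulation (2 nursing, 1 therapist, 1 doctor; Study Configuration).

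- Simulations: 4 × 2 × 4 = 32.
- Participants: 32 × 4 = 128.
- Focus groups, two per day: 4 × 2 × 2 = 16.

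These agree with Study Duration, which says enrolment "will be completed within 6 months when up to 32 simulations and up to 16 focus groups have been analysed", and with the 128 in the Synopsis.

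**Step 2: count the runs that start after disclosure at the same Trust.** On each day the simulations run at 08.30–09.00, 09.30–10.00, 13.30–14.00 and 14.30–15.00, with focus groups at 10.00–12.00 and 15.00–17.00. A run counts if an earlier group at that Trust has been re-consented before it starts. Day 1 disclosure counts for day 2.

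| When a group is told | Runs per Trust before any disclosure | Runs after disclosure, 4 Trusts | Participants in those runs |
|---|---|---|---|
| Straight after its own simulation | 1 of 8 | 7 × 4 = 28 of 32 (87.5%) | 28 × 4 = 112 of 128 |
| At the start of the focus group | 2 of 8 | 6 × 4 = 24 of 32 (75%) | 24 × 4 = 96 of 128 |

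With fewer Trusts the proportions stay at 7 of 8 and 6 of 8. On either reading, every day 2 run follows disclosure to up to 4 × 4 = 16 colleagues. If only same-day disclosure is counted, over 4 × 2 = 8 site-days, the totals are 3 × 8 = 24 of 32 and 2 × 8 = 16 of 32.

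**Step 3: which reading fits the timetable?** Re-consent takes 5 minutes. Four private re-consents, one after another, take 4 × 5 = 20 minutes and fit the 30 minutes between 09.00 and 09.30. The second simulation ends at 10.00, exactly when the focus group starts, so there is no slot there for the first group. The timetable therefore favours 28. Even on the other reading, the first group has already been through the simulated fall before the second begins.

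**Step 4: set the form beside the criteria.** The form is for checking the inclusion criteria, and the protocol contains only one set. Three of its four role criteria name falls. No section provides a neutral version for volunteers. The Recruitment section also promises that the investigator will brief participants on everything that bears on taking part, which sits awkwardly with withholding the topic. The number who would use the QR code rather than email, WhatsApp or phone is not given, so exposure by this route cannot be sized.

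**The case against.** The strongest reply is that the simulation is not the main source of data. The Informed consent section says it exists to prompt discussion, and that the findings come chiefly from the focus group. By then everyone knows the topic by design. This stands, and it limits the harm. It does not remove it: observations inform the discussion, the critical decision session (step 13) reconstructs the simulation, and step 18 draws themes from simulations as well as focus groups.

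Second, a reader might infer that the form does show the fall-worded criteria. The documents do not support that. The form is not reproduced, the study titles are neutral, and the investigator intends neutral language before the simulation. What stands is that nothing says how the form checks these criteria without naming falls. Nor is there evidence that the poster or invitation email mentions falls.

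Third, a reader might take 28 of 32 as the number of unmasked simulations, or conclude that bias grows with run order. Neither follows. The count is of opportunities for word of mouth, and the documents give no leakage rate.

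Fourth, the confidentiality request covers any information, which would include the topic, and breaches have an escalation route. That deserves credit. But it is the only barrier, and the plan itself allows that it may fail.

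Finally, concealment is worded as a preference, and participants may withdraw at re-consent, although data already collected are kept. The plan would not collapse if some staff guessed the topic.

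**Conclusion.** The concern holds in a limited form. Following the plan as written can undercut its own concealment by two routes, and no data item would show whether it had.

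- **Form:** it may reveal the topic to volunteers who use it. This is inferred from its stated purpose and the only criteria available; its size is unknown.
- **Timetable:** at full size, 24 to 28 of 32 simulations start after colleagues at the same Trust have been told. The upper figure assumes disclosure straight after each simulation; the lower assumes it waits until the focus group. Both count day 1 disclosure for day 2.

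The effect falls mainly on the simulation observations and the decision timeline. A reader might conclude that the focus-group findings are invalid; the documents do not support that. This is something the sponsor should fix, not a bar to running the study.

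**What to change.** 1. **Screening.** Have the form ask only neutral facts: role, ward type and direct patient contact. The investigator then applies the existing fall-role criteria, unchanged, to the answers.
2. **Confidentiality.** State in the existing agreement that topic and scenario are not to be disclosed until that Trust's second day has ended. Keep a finished group apart from the next where the timetable allows.
3. **Prior awareness.** At re-consent, ask each participant whether they knew or suspected beforehand that the simulation would involve a fall. Record the answer and run order in the Trial Recruitment Log.
4. **Interpretation.** Describe prior awareness when interpreting the observations and decision timelines. A formal comparison with and without forewarned runs is not suitable, because each focus-group dataset merges two simulations.

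The third item matters most: leakage cannot be fully prevented, but it can be recorded. The cost is a reworded form, a sentence in the agreement and one question at an existing step. The downside is that the investigator, not the volunteer, does the final screening.

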FULL TITLE OF THE CLINICAL STUDY

What is the clinical experience of maintaining patient safety in hospital in patients with temporary or permanent loss of cognitive function? A Mixed Methods Study

Protocol Final Version 1.0 06.11.2024
(Last updated 11.05.2026)

Short title: Clinical Experience of Maintaining Patient Safety in Hospital

Acronym: CEMPSIH

IRAS Project ID: 347285

Study Sponsor: University of Nottingham

Sponsor reference: **24065**

Funding Source: This study is part of a PhD study funded by a scholarship awarded by the Engineering and Physical Sciences Research Council (EPSRC).

STUDY PERSONNEL AND CONTACT DETAILS

Sponsor: Contact name	University of Nottingham [name] Head of Research Integrity, Governance & Compliance University of Nottingham [name] [contact]
Chief investigator:	Asst. [name] Associate [name] Human Factors Research Group Faculty of Engineering University of Nottingham Phone: Email: [contact]
Co-investigators:	
[name] [name] Principal Research Fellow, NIHR MindTech Research Centre Institute of Mental Health Email: [contact]
 
[name] Principle Research Fellow Centre for Rehabilitation and Ageing Research School of Medicine, Queens Medical Centre Email: [contact]
 
[name] Student ID: [name] Human Factors Research Group [contact] Email: [contact]

Study Coordinating Centre:	Human Factors Research Group Faculty of Engineering, University of Nottingham, [name]

SYNOPSIS

Title	What is the clinical experience of maintaining patient safety in hospital in patients with temporary or permanent loss of cognitive function? A Mixed Methods Study
Short title	Clinical Experience of Maintaining Patient Safety in Hospital (CEMPSIH)
Chief Investigator	Associate [name]
Objectives	To test whether there is a universal professional experience of maintaining patient safety in hospitals, with patients who have impaired cognitive function
Study Configuration	Mixed Methods, Multi-centre, Exploratory Sequential Strategy
Setting	Secondary care - Acute Hospital Trusts
Number of participants	128 participants overall. Up to 32 participants per Hospital (16 Nursing staff, 8 Therapists and 8 Medical Doctor or associates)
Eligibility criteria	Direct patient facing healthcare workforce responsible for managing and preventing accidental falls in the NHS.

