- To disprove the null hypothesis that “there is no universal clinical experience of accidental fall prevention in hospitals with patients who have impaired cognitive function”.

SECONDARY OBJECTIVES

[figure not shown]
- To inductively generate a questionnaire to be distributed to healthcare professionals and care workers in a future study.
- To gather an evidence base for the co-created design and testing of fall prevention interventions as part of the longer term PhD project

The investigator has completed the HRA tools which have confirmed the study is classed as research and that it does not require NHS REC review. The investigator has also successfully undertaken the Good Clinical Practice training to provide public assurance that the rights, safety and wellbeing of research participants are protected and that research data are reliable.

STUDY DESIGN

STUDY CONFIGURATION

This is a multi-centre qualitative study utilising a purposive sampling strategy. Healthcare workers directly involved in preventing falls in hospital will be invited to contribute to the study via an email from their ward manager or clinical lead. Participants will be asked to respond directly to the researcher to indicate their interest in the study. They will be selected to ensure Medical and Surgical wards are represented to ensure generalisability of outcomes. Overall aim will be for up to 16 participants from the nursing team, registered and unregistered, up to 8 therapist participants and up to 8 doctors (*Figure 1- Participant Study Flowchart*).

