- Any healthcare professional or associated support staff involved in putting fall prevention measures in place in an acute ward environment
- Any healthcare professional or associated support staff involved in caring for patients and their relatives after an accidental fall in an acute ward environment
- Ability to give informed consent

Exclusion criteria

- Any healthcare worker with no medical or surgical ward experience
- Any healthcare worker under the age of 18 years old
- Any healthcare worker working exclusively in Critical Care or high dependency units or Paediatrics as countermeasures and levels of observation are different in these areas and have separate guidance and policies.

Expected duration of participant participation

Study participants will be participating in the study for a total of 4 hours over a period of 3 months.

Participant Withdrawal

Participants will withdraw from the study:-

- if consent is withdrawn
- if they become unwell
- If it is not safe for them to continue due to safety reasons outlined in the simulation risk assessment

Participants may be withdrawn from the study either at their own request or at the discretion of the Investigator. The participants will be made aware that this will not affect their employment rights. Participants will be made aware (via the information sheet and consent form) that should they withdraw the data collected to date cannot be erased and may still be used in the final analysis.

Informed consent

All participants will provide written informed consent. The Informed Consent Form will be signed and dated by the participant before they enter the trial. The Investigator will explain the details of the trial and provide an opportunity to go over any questions from the Participant Information Sheet that they received with the invite, ensuring that the participant has sufficient time to consider participating or not. The Investigator will answer any questions that the participant has concerning study participation.

Informed consent will be collected from each participant before they participate in any part of the study. One copy of this will be kept by the participant, one will be kept by the Investigator.

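### The objectives claim a universal experience in hospitals, but the sample can support a conclusion only for adult medical and surgical wards

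*Combined protocol and SAP*

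**What the plan says.** The Primary Objective section sets out to disprove the null hypothesis that "there is no universal clinical experience of accidental fall prevention in hospitals with patients who have impaired cognitive function". The Synopsis gives the objective as "To test whether there is a universal professional experience of maintaining patient safety in hospitals, with patients who have impaired cognitive function". Both are restricted by type of patient; neither is restricted by type of ward. The Synopsis lists the setting as "Secondary care - Acute Hospital Trusts".

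The sample is narrower. Under Recruitment, "Participants will be recruited from medical and surgical wards at up to 4 acute Trusts". Two of the exclusion criteria bear on scope:

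- "Any healthcare worker with no medical or surgical ward experience"
- "Any healthcare worker working exclusively in Critical Care or high dependency units or Paediatrics", with the reason "as countermeasures and levels of observation are different in these areas and have separate guidance and policies"

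The Study Configuration section says that medical and surgical wards are both to be represented so that the outcomes generalise, but it does not say to which population. The Study Regimen ends with a synthesis of general views across all sessions. The sample size section continues sampling until recurring themes indicate whether experiences are homogeneous. None of these sections says where a finding of homogeneity would apply.

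**The concern.** In many qualitative studies, a sample narrower than the question calls only for a routine caveat on transferability. Here the claim itself is universality, and such a claim fails if any part of the population it covers differs. Leaving out parts of the hospital therefore bears directly on the hypothesis, all the more so because the stated reason is that fall-prevention practice is different there.

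The wording will be carried forward. The secondary objectives use the results to build a questionnaire for healthcare professionals and care workers, and to form an evidence base for designing and testing fall-prevention interventions. If the study reports a universal experience in hospitals, both could be taken to cover areas from which exclusive staff were never sampled.

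**Working it through.** No alpha, power or effect size is stated, so no sample-size formula applies. The check has two parts: the plan's counts, then a comparison of the claim with the sample.

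**Counts**

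Inputs, from Study Configuration and its participant table: 1 doctor + 1 therapist + 2 nursing staff = 4 per simulation; 4 simulations a day; 2 days; up to 4 hospitals; 2 simulation groups per focus group.

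- Simulations: 4 × 2 × 4 = 32
- Participants: 4 × 32 = 128, or 128 / 4 = 32 per hospital
- Per hospital by profession (8 simulations each): 2 × 8 = 16 nursing staff, 1 × 8 = 8 therapists, 1 × 8 = 8 doctors
- Focus-group datasets: 32 / 2 = 16

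These match the plan's 128 participants, 32 simulations and 16 datasets. The point does not depend on any of them.

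**Claim against sample**

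| Element | Scope by ward type | Where |
|---|---|---|
| Null hypothesis | Hospitals, no limit | Primary Objective |
| Synopsis objective | Hospitals, no limit | Synopsis |
| Setting | Acute Trusts | Synopsis |
| Recruitment | Medical and surgical wards | Recruitment |
| Ward experience required | Medical or surgical | Exclusion criteria |
| Left out if working only there | Critical care, high dependency, paediatrics | Exclusion criteria |
| Where the conclusion applies | Not stated | Study Regimen; Analyses |

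**Reasoning**

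1. By the exclusion criteria, 0 of the up to 128 places can go to staff who work only in the three named areas.
2. All 16 datasets therefore come from staff with medical or surgical ward experience.
3. Suppose all 16 agree completely. That is evidence of a shared experience among such staff. It says nothing direct about those who were ineligible.
4. Extending the result to them would require assuming that their experience is similar. The protocol offers no support for that assumption, and its reason for the exclusion is that countermeasures, observation and policies differ there.
5. So the most favourable possible result still falls short of the hypothesis as worded. It would support the same hypothesis worded for the wards sampled.

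**The case against.** The strongest reply is that the population is in plain view. The objectives are limited to patients with impaired cognitive function, the setting is acute Trusts, the inclusion criteria refer to standard care or acute wards, and recruitment is openly from medical and surgical wards. An objective need not repeat every eligibility criterion. The choice of wards also has its own justification: the Recruitment section selects them for their regular exposure to older patients and others at high risk of falls, and the background rests on the same age groups. Paediatrics lies outside that rationale.

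Much of this stands. It shows that the sample is sensible and that the exclusion should stay. It does not show that the sample can carry the wider claim. The acute setting narrows the scope only in part, since critical care and high dependency had to be excluded separately.

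A reader might go further and infer that a finding of universality would be an artefact, true only because differing areas had been removed, or that the eligibility text contradicts the hypothesis. The documents do not support this, for three reasons:

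- The stated differences concern countermeasures, observation, guidance and policies. Staff working under different policies may still share an experience.
- Only staff working exclusively in those areas are excluded. Those who also work elsewhere and have medical or surgical ward experience may take part.
- The exclusion does not guarantee agreement. Homogeneity could still fail between professions, between medical and surgical wards, or between hospitals, and the sample size section allows for either outcome.

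**Conclusion.** The point holds as a mismatch of scope: both objectives claim more than the design can establish. A positive result would support a shared experience among staff of medical and surgical wards in acute hospitals, not across hospitals. The study remains valid for the wards it samples.

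The mismatch cannot be put in numbers. It consists of three named areas whose exclusive staff contribute nothing to the data, with no figure in the documents for how large a share of hospital staff they are. The conclusion assumes that *in hospitals* is meant as written and that no limit on the conclusion is stated elsewhere; none appears in the sections available for review.

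The argument concerns ward type only. It gives no ground for confining the conclusion to the participating Trusts. How far a purposive sample from up to 4 Trusts transfers to other acute hospitals is a separate question.

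**What to change.** Keep the exclusion criteria as they are, and make two changes of wording:

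1. In the Synopsis objective and the Primary Objective, replace *in hospitals* with *on adult medical and surgical wards in acute hospitals*.
2. In the Analyses section, add a sentence stating that a finding of homogeneity will not be extended to critical care, high dependency or paediatrics.

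Recruitment, sessions, data collection and coding do not change. The cost is a wording amendment and a narrower headline claim.
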